4.0 Introduction

This statistical analysis plan (SAP) provides a detailed elaboration of the statistical analyses of the efficacy and safety data as specified in the final protocol of Study 1925-201-008 (amendment 1 version dated 25 September 2020). Specifications of tables, figures, and data listings are contained in a separate document.

This is a phase 2, multi-center, randomized, double-blind, placebo-controlled, dose-ranging study in patients 55-90 years of age who are scheduled to undergo open-chest cardiac surgery.

The length of this study will be 367 days, not including the screening visit, which may occur up to 28 days before the first study day (randomization). Signed informed consent from the participant will be obtained before any study-related procedures are begun. Patients meeting the inclusion/exclusion criteria will be randomized (1:1:1 ratio) to one of three treatment arms at the end of the screening period. Primary and secondary efficacy assessments will be assessed for 30 days post-surgery. Additional efficacy and exploratory assessments will be assessed through Day 367 post-surgery. All participants will be followed through Day 367 for safety assessments. Every attempt will be made for participants who prematurely discontinue from the study, regardless of cause, to be seen for a final evaluation.

The study schema is presented below.

D = study day; TC = telephone call; U = units; V = Visit

a Hospital discharge could take more than 6 days.

The schedule of evaluations is presented in the Table 4–1 below.

Page 7

Table 4–1Schedule of Evaluations: Study 1925-201-008

Study Period	Screening ^a	Days 1 to 60						Day 61 through Day 360								
Visit Number	V1	V2	V3	V4 ^b	V5 ^b	V6 ^b	V7 ^b	TC1	V8	V9	V10	V11	V12	V13	TC2	Early
Day Number	(up to 28 days)	D1	D2	D3	D4	D5	D6	D14	D30	D60	D90	D180	D270	D360	D367 ^d	Disc
Visit Windows	-	-	-	-	-	-	-	± 3d	± 3d	± 3d	± 7d	± 7d	± 7d	± 7d	V13 + 7d (+ 7d)	-
Informed consent	Х															
Inclusion and exclusion criteria	Xe	Х														
Demography	Х															
Physical examination	Х								Х					Xf		Х
Medical history	X															
Urine pregnancy test (for women of childbearing potential) ^{e,g}	Х	x														
Laboratory assessments ^{e,h}	Х	Х					Х		Х	Xi	Xi			Xi		Х
Sample collection for biomarker assessment ^e		Х	х	Х	Х											
12-lead ECG ^j	Х	Х	Х	Х	Х	Х	Х		Х	Xk	Xk	Xk	Xk	Xk		Х
ECG patch		Х	Х	Х	Х	Х	Х	Х	X ¹	X ^m	Х					
Vital signs ^{e,n}	Х	Х	Х	Х	Х	Х	Х		Х	Х	Х	Х	Х	Х		Х
Height	Х															
Body weight and abdominal circumference	Х													Х		Х
Dispense AF symptom diary and train participant on proper use ^o	Х															
AF symptom diary review ^o		Х	Х	Х	Х	Х	Х	Х	Х	Х	Х	Х	Х	Х	Х	Х
Randomization		Х														
Study intervention ^p		Х														
Assessment of fat pads and injection procedure		Х														
AE/SAE review ^q	Х	Х	Х	Х	Х	Х	Х	Х	Х	Х	Х	Х	Х	Х	Х	Х
PFT ^r	Х								X							
Concomitant medication and concurrent procedure review ^e	X	X	Х	Х	Х	Х	Х	X	X	Х	X	Х	Х	Х	Х	Х

Study Period	Screening ^a				D	avs 1 to	60					Day 61	through	Dav 360		
Visit Number	V1	V2	V3	V4 ^b	V5 ^b	V6 ^b	V7 ^b	TC1	V8	V9	V10	V11	V12	V13	TC2	Early
Day Number	(up to 28 days)	D1	D2	D3	D4	D5	D6	D14	D30	D60	D90	D180	D270	D360	D367 ^d	Disc ^c
Visit Windows	-	-	-	-	-	-	-	± 3d	± 3d	± 3d	± 7d	± 7d	± 7d	± 7d	V13 + 7d (+ 7d)	-
AFEQT	Х								Х		Х	Х				X ^s
AFSS	Х								Х		Х	Х				Xs
DASI	Х								Х		Х	Х				Xs
EuroSCORE II ^t	Х															
SF-12v2	Х								Х		Х	Х				Xs
EQ-5D-5L	Х								Х		Х	Х				Xs
Record discharge from ICU		Х	Х	Х	Х	Х	Х									
Record discharge from hospital			Х	Х	Х	Х	Х									
Record any additional healthcare resource utilization								Х	Х	Х	Х	Х	Х	Х	Х	Х
Serum sampling for immunogenicity assessment ^u	Х								Х		Х					

Allergan PLC AGN-151607

AE = adverse event; AF = atrial fibrillation; AFEQT = Atrial Fibrillation Effect on Quality-of-life Questionnaire; AFSS = University of Toronto Atrial Fibrillation Severity Scale; D(d) = day; DASI = Duke Activity Status Index; Disc = discontinuation; ECG = electrocardiogram; EQ-5D-5L = A measure of health-related quality of life developed by the EuroQol Group; FU = follow-up; ICU = intensive care unit; PFT = pulmonary function test; SAE = serious adverse event; SF-12v2 = Short Form-12 Health Survey, version 2; TC = telephone call; V = visit

a Screening and randomization activities can occur on the same day. If screening and randomization occur on the same day, all assessments for Visit 1 and Visit 2 should be completed. Duplicate assessments (eg, laboratory assessments) do not have to be completed twice; please note a 12-lead ECG is required both before and after surgery.

b These visits are optional and are only required if the participant is still hospitalized. Participants may remain in the hospital beyond Day 6, based on the recovery from surgery. The study visit procedures will have to be performed each day until discharge.

- c In case of early discontinuation, attempts will be made to follow-up with the participant.
- d Day 367 must be at least 7 days and should be no more than 14 days after Visit 13 (Day 360).
- e On Day 1, assessments to be performed prior to surgery.
- f Physical examinations should be conducted where feasible. If the participant cannot attend the study visit, then the physical examination can be omitted, after sponsor approval.
- g Local urine testing will be standard for the protocol unless serum testing is required by local regulation or IRB/IEC.
- h Laboratory assessments (hematology, chemistry, coagulation and urinalysis) to be performed at screening, Day 1 and day of discharge. The day of discharge can be from Day 3 onwards.
- i Laboratory assessments should be conducted where feasible. If the participant cannot attend the study visit and/or an in-home assessment is not feasible, then the laboratory assessments can be omitted, after sponsor approval.

Allergan PLC AGN-151607

- j On Visit 2, Day 1, two 12-lead ECGs will be performed; 1 before surgery and 1 after surgery. PFT should be performed at a reasonable time apart from vital signs and ECG to avoid confounding ECG and vital signs data.
- k 12-lead ECGs should be conducted where feasible. If the participant cannot attend the study visit and/or an in-home assessment is not feasible, then the 12-lead ECG can be omitted, after sponsor approval.
- 1 ECG patch must be worn for a full 30 days post-surgery, even if Day 30 visit occurs prior to Day 30 due to window allowance.
- m ECG patch must be used during the first 7 days following Day 60, Day 90, Day 180, Day 270 and Day 360 visits.
- n Vital signs taken after a participant has been in a resting position for a minimum of 5 minutes; include blood pressure, pulse, respiration rate, and body temperature. On Visit 2, Day 1, vital signs will be measured before and after surgery.
- o AF symptom diary must be used for first 30 days after surgery (or until early discontinuation if before Day 30) and during the first 7 days following Day 60, Day 90, Day 180, Day 270 and Day 360 visits. The diary should be returned to the site and be part of the medical records.
- p Unblinded site pharmacist or designee will prepare drug; injected by investigator who is blinded to study intervention.
- q Method of detecting AEs and SAEs: care will be taken not to introduce bias when detecting AEs and/or SAEs. Open-ended and nonleading verbal questioning of the participant is the preferred method to inquire about AE occurrences.
- r Pulmonary function to be assessed using a spirometer and will include forced vital capacity (FVC) and the forced expiratory volume in 1 second (FEV1), 3 seconds (FEV3) and 6 seconds (FEV6). Note, if local policies contraindicate or prohibit PFT assessments due to potential for viral spread or microbial precautions, then the PFT is not required after explicit approval from the sponsor.
- s If participant withdraws after Day 180, these early discontinuation procedures will not be performed.
- t Impaired prognosis defined as EuroSCORE II > 7% perioperative mortality at screening is exclusionary.
- u Serum collection should be conducted where feasible. If the participant cannot attend the study visit and/or an in-home assessment is not feasible, then the serum collection can be omitted, after sponsor approval.

5.0 Objectives

5.1 Primary Efficacy Objectives

• To compare the efficacy of AGN-151607 with placebo to prevent post-operative atrial fibrillation (POAF) in participants who are undergoing open-chest cardiac surgery.

5.2 Secondary Efficacy Objectives

- To compare the efficacy of AGN-151607 with placebo to reduce atrial fibrillation (AF) burden in participants who are undergoing open-chest cardiac surgery.
- To compare the efficacy of AGN-151607 with placebo to prevent POAF using alternative definitions for POAF in participants who are undergoing open-chest cardiac surgery.

5.3 Safety Objectives

• To compare the safety of AGN-151607 with placebo in participants undergoing open-chest cardiac surgery.

5.4 Additional Objectives

• To compare the clinical benefit of AGN-151607 with placebo in participants who are undergoing open-chest cardiac surgery.

5.5 Exploratory Objectives

- Assessment of fat pads and injection procedure
- Quality of life outcomes
- Assessment of biomarkers

6.0 Patient Populations

6.1 Modified Intent-To-Treat Population

The Modified Intent-to-Treat (mITT) Population will consist of all randomized participants who received study treatment and had at least 1 post-dose ECG (by ePatch) by Day 30 post-surgery. Analyses will be based on randomized treatment.

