f Physical examinations should be conducted where feasible. If the participant cannot attend the study visit, then the physical examination can be omitted, after sponsor approval. g Local urine testing will be standard for the protocol unless serum testing is required by local regulation or IRB/IEC.

h Laboratory assessments (hematology, chemistry, coagulation and urinalysis) to be performed at screening, Day 1 and day of discharge. The day of discharge can be from Day 3 onwards.

i Laboratory assessments should be conducted where feasible. If the participant cannot attend the study visit and/or an in-home assessment is not feasible, then the laboratory assessments can be omitted, after sponsor approval.

j On Visit 2, Day 1, two 12-lead ECGs will be performed; 1 before surgery and 1 after surgery. PFT should be performed at a reasonable time apart from vital signs and ECG to avoid confounding ECG and vital signs data.

k 12-lead ECGs should be conducted where feasible. If the participant cannot attend the study visit and/or an in-home assessment is not feasible, then the 12-lead ECG can be omitted, after sponsor approval.

ECG patch must be worn for a full 30 days post-surgery, even if Day 30 visit occurs prior to Day 30 due to window allowance.

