### 8.2.3. Electrocardiograms

- Sites or designee shall transmit all study-required ECGs obtained to the ECG vendor. If multiple ECGs have been obtained for the same participant on the same date, the first readable ECG shall be entered as the visit ECG, and all others shall be entered as unscheduled. All readable ECGs received by the vendor shall be sent for ECG vendor, cardiologist over-read. The sponsor will receive all ECG data, including vendor cardiologist assessments, in the data transfer, including those ECGs that could not be evaluated.
- On Visit 2, Day 1, two 12-lead ECGs will be performed; 1 before surgery and 1 after surgery.
- A 12-lead ECG will be obtained in the supine or semi-recumbent position as outlined in the SoA (see Section 1.3) using an ECG machine that automatically calculates the heart rate and measures PR, QRS, QT, and QTc intervals.
- The X-axis speed will be a standard 25 mm per second; the ECG tracing will be kept at the study site. Measurements will be recorded for the following parameters in lead II or lead III: heart rate, PR interval, QRS duration, QT interval, and QTc. All ECGs will be clinically interpreted by the investigator or sub-investigator.

AGN-151607

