# 9.3. **Populations for Analyses**

A study participant is enrolled in the study the moment he or she has signed the ICF.

The analysis populations will consist of participants as defined below:

- The modified intent-to-treat (mITT) population will consist of all randomized participants who received study intervention and had at least 1 post-dose ECG by Day 30 post-surgery. Analyses will be based on randomized intervention.
- The safety population will consist of all participants who received study intervention. Analyses will be based on actual intervention received.

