#### 9.4.1. Efficacy Analyses

All efficacy analyses will be based on the mITT Population.

Each participant will be continuously monitored through Day 30, and during the first 7 days following Day 60, Day 90, Day 180, Day 270 and Day 360 visits, for all occurrences of AF episodes as well as the length of time spent in each of the corresponding AF episodes using ECG patches placed on the upper region of the participant's chest.

The ECG measurements collected for AF episodes post-surgery will be used to provide *9* different definitions for POAF for use in statistical analyses, namely:

- 1. At least 1 continuous AF episode  $\geq$  30 seconds
- 2. At least 1 continuous AF episode  $\geq$  2 minutes
- 3. At least 1 continuous AF episode  $\geq$  5 minutes
- 4. At least 1 continuous AF episode  $\geq$  30 minutes
- 5. At least 1 continuous AF episode  $\geq$  1 hour
- 6. At least 1 continuous AF episode  $\geq$  4 hours

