10.0 Efficacy Analyses

All efficacy analyses will be based on the mITT Population, unless otherwise specified. Note that the use of the phrase "AF" or "AF episode" in the section and subsections below implies an occurrence of either atrial fibrillation or atrial flutter. Other analyses will be conducted to assess only atrial fibrillation, only atrial flutter, only atrial tachycardia, and a combination of either atrial fibrillation, atrial flutter, or atrial tachycardia.

Each participant will be continuously monitored for the first 30 days post-surgery, and during the first 7 days following Day 60, Day 90, Day 180, Day 270, and Day 360 visits, for all occurrences of AF episodes as well as the length of time spent in each of the corresponding AF episodes using ECG patches (ePatch) placed on the participant's chest.

Even though each participant is expected to wear the epatch for the first 30 days post-surgery, and during the first 7 days following Day 60, Day 90, Day 180, Day 270 and Day 360 visits, all analyzable data (interpretable) collected from the epatch will be included in the analysis regardless of any deviations from these timeframes.

The ECG measurements collected for AF episodes post-surgery will be used to provide 10 different definitions for POAF for use in statistical analyses, namely:

- 1. at least 1 continuous AF episode \geq 30 seconds
- 2. at least 1 continuous AF episode \geq 2 minutes

- 3. at least 1 continuous AF episode \geq 5 minutes
- 4. at least 1 continuous AF episode ≥ 6 minutes
- 5. at least 1 continuous AF episode \geq 30 minutes
- 6. at least 1 continuous AF episode \geq 1 hour
- 7. at least 1 continuous AF episode \geq 4 hours
- 8. at least 1 continuous AF episode ≥ 6 hours
- 9. at least 1 continuous AF episode \geq 12 hours
- 10. at least 1 continuous AF episode \geq 24 hours

Based on information collected from continuous monitoring for all occurrences of AF during the first 30 days post-surgery, the percent of time spent in AF (hereinafter referred to as AF Burden) during the first 30 days post-surgery will be calculated as (the total time spent in AF during the first 30 days post-surgery divided by the total time of analyzable data obtained from the ECG patch during the first 30 days post- surgery) multiplied by 100.

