In addition, similar definitions of POAF as well as the derivation of the AF Burden will be obtained based on continuous monitoring of all occurrences of AF during the first 7 days following Day 60, Day 90, Day 180, Day 270, and Day 360 visits.

All analyses using ECG patch data will be based on observed data; no imputation will be performed on missing data from the ECG patch device. Descriptive statistics of the total time of analyzable data obtained from the ECG patch during the first 30 days post- surgery will be presented by treatment group. Similar statistics will be presented for each of the first 7 days following Day 60, Day 90, Day 180, Day 270, and Day 360 visits.

Unless otherwise stated, the ICU admission date for the index surgery (initial care of indication under study) will be used as reference timepoint to establish if an event occurred within a specified timeframe "post-surgery". For example, the occurrence of AF during the first 30 days post-surgery will imply the occurrence of AF during the first 30 days following the initial ICU admission date.

In general, continuous and ordinal variables will be summarized by descriptive statistics and will include sample size, mean, standard deviation, median, minimum, and maximum. Nominal variables will be summarized by frequency and percentage.

Inferential analyses will include 3 treatment groups: Placebo, 125 U, and 250 U of AGN-151607. Each dose level of AGN-151607 (125 U and 250 U) will be separately compared to placebo. All treatment comparisons will be made at the $\alpha = 0.05$ level (2-sided). To control for multiplicity in comparing 2 doses of AGN-151607 with placebo, the primary efficacy variable will be tested sequentially by first comparing the high dose to placebo. The low dose will be compared to

placebo only if the comparison to the high dose is found to be statistically significant. There will be no adjustment for multiple comparisons for all other efficacy variables.

Mis-stratified participants, if any, will be analyzed based on the correct stratification group [type of surgery (presence or absence of valve surgery) and age group (< 65 or ≥ 65 years)], not the stratification group to which the participants were assigned at the time of randomization.

Unless otherwise stated, the use of the phrase "percentage of participants" for any efficacy variable in the sections below assumes the variable is a binary categorical response outcome.

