- A negative binomial (NB) regression model will be used to model the number of AF events (using \geq 30 seconds definition of AF) within 30 days post-surgery, with treatment, type of surgery, and age group as factors and log(total analyzable time) as the offset in the model. A zero-inflated negative binomial (ZINB) regression model will also be estimated with treatment, type of surgery, and age group as factors in both the main and zero-count models and log(total analyzable time) as the offset. If p < 0.05 for the Scaled Pearson chi-square goodness of fit statistic for the NB model (suggesting overdispersion may be present), then the ZINB model will be considered the primary analysis; otherwise, the NB model will be considered the primary analysis. Sensitivity analyses of the number of AF events using Poisson regression and zero-inflated Poisson regression using similar models will be performed. Least squares (LS) mean differences and incidence rate ratios with 95% CIs will also be performed based on the SEA-30 set using the same models.
- The win ratio unmatched approach (Pocock et. al., 2012) will be used to analyze the following composite endpoint:
 - 1. Death
 - 2. Stroke
 - 3. All-cause 30-day rehospitalization
 - 4. Use of pharmacologic or procedural intervention of interest due to AF
 - 5. Hospital length of stay

The components of the endpoints are listed in order of clinical importance. The win ratio, with the associated 95% CI and p-value will be presented for the composite endpoint, as well as for each of the component endpoints. Two win ratios analyses will be performed. The first will analyze binary outcomes for each of the components (with the fifth component being "Hospital length of stay > median hospital length of stay for the total study population"). The second will analyze time-to-event outcomes for each of the components (with the time-to-first-event used for components with multiple events experienced, and with the fifth component being time-to-hospital-discharge from initial care). A list of Medical Dictionary for Regulatory Activities (MedDRA) preferred terms for stroke will be provided by the clinical team. All-cause 30-day rehospitalization includes any hospitalization within 30 days of (first) discharge from the hospitalization for initial care.

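### SAP 6.1 restricts mITT to participants with an ePatch recording without declaring the change, and that set also governs the win ratio and other endpoints that need no patch

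*SAP*

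**What the plan says.** Protocol 9.3 defines mITT as randomised participants who "received study intervention and had at least 1 post-dose ECG by Day 30 post-surgery". It does not restrict the type of ECG. Protocol 8.2.3 and the schedule of activities require a 12-lead ECG after surgery on the day of dosing ("On Visit 2, Day 1, two 12-lead ECGs will be performed; 1 before surgery and 1 after surgery"), and further 12-lead ECGs at the in-hospital visits.

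SAP 6.1 has the same structure but admits participants who "received study treatment and had at least 1 post-dose ECG (by ePatch) by Day 30 post-surgery". SAP 16.0 lists three changes from the protocol, and this is not one of them. The version history in SAP 17.0 does not mention it either.

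Both documents make mITT the efficacy population: Protocol 9.4.1 ("All efficacy analyses will be based on the mITT Population") and SAP 10.0 ("All efficacy analyses will be based on the mITT Population, unless otherwise specified"). The other efficacy sets named in the SAP (SEA-7, SEA-30 and the beta-blocker-withdrawn set) also require ePatch data. SAP 10.3 and 10.4 name no wider set for length of stay, rehospitalisation, resource use, AF interventions, the win ratio or quality of life. For the win ratio, SAP 10.3 puts death first and states: "The components of the endpoints are listed in order of clinical importance".

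SAP 7.0 counts the Safety and mITT populations by arm, but tabulates and lists discontinuations and their reasons for mITT only.

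**The concern.** Having an ePatch recording is a condition met, or not met, after randomisation. For patch-derived endpoints that is hard to avoid, because nothing can be computed without a recording and SAP 10.0 states that "no imputation will be performed on missing data from the ECG patch device". For endpoints taken from hospital records, vital status, medication records or questionnaires, the condition removes people whose outcome is known.

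The win ratio is the clearest case. A dosed participant who dies before any patch recording has had the worst outcome in the hierarchy, yet is not in the comparison. SAP 10.3 shows that such deaths were meant to count: it ranks death first, and it has a rule for deriving length of stay when a participant dies in hospital or in the ICU. SAP 6.1 works against that intent, and a reader who checks SAP 16.0 for departures from the protocol would not find it.

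**Working it through.** **Step 1: who is lost because of the ePatch condition?**

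| Dosed participant | Protocol 9.3 mITT | SAP 6.1 mITT |
|---|---|---|
| At least one ePatch recording by Day 30 | in | in |
| 12-lead ECG after surgery, no ePatch recording by Day 30 | in | out |
| No post-dose ECG of any kind | out | out |

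Only the middle row is due to the SAP. The bottom row is excluded under both documents, so going back to the protocol wording would not recover a death before any post-dose ECG.

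**Step 2: is there a stated figure to check?** Neither document gives the number of dosed participants without patch data. The only related figure is power of about 80% for 47.8% versus 27.8% with 100 per arm (SAP 13.0). With a continuity correction:

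- d = 0.200, 1/n = 0.010, pooled p = 0.378
- SE0 = √(2 × 0.378 × 0.622 / 100) = 0.0686
- SE1 = √((0.478 × 0.522 + 0.278 × 0.722) / 100) = 0.0671
- power = Φ((0.200 − 0.010 − 1.96 × 0.0686) / 0.0671) = 79.6%

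The stated figure reproduces. With 97 or 95 analysed per arm it becomes 78.3% or 77.3%. Power is not the issue.

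**Step 3: death component of the win ratio (illustration).** Assume 110 per arm (330/3) and the binary version. A ratio above 1 favours the active arm.

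ratio = (placebo deaths × active survivors) / (active deaths × placebo survivors)

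| Deaths, active v placebo | Deaths lost for lack of a patch recording | Calculation | Ratio |
|---|---|---|---|
| 3 v 3 | none | (3×107)/(3×107) | 1.00 |
| 3 v 3 | 1 active | (3×107)/(2×107) | 1.50 |
| 3 v 3 | 2 active | (3×107)/(1×107) | 3.00 |
| 3 v 3 | 1 placebo | (2×107)/(3×107) | 0.67 |
| 3 v 3 | 1 in each arm | (2×107)/(2×107) | 1.00 |
| 4 v 2 | none | (2×106)/(4×108) | 0.49 |
| 4 v 2 | 2 active | (2×106)/(2×108) | 0.98 |

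**Step 4: the composite (illustration).** In the 3 v 3 case, death decides 321 + 321 = 642 of 110 × 110 = 12,100 pairs, or 5.3%. Now add only the length-of-stay tier, assuming half of each arm is above the median. Among the 107 × 107 = 11,449 survivor pairs, a quarter (2,862) are wins and a quarter are losses. Pairs in which both died are left as ties.

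- none lost: (321 + 2,862)/(321 + 2,862) = 1.00
- 1 active death lost: (321 + 2,862)/(214 + 2,862) = 1.03
- 2 active deaths lost: (321 + 2,862)/(107 + 2,862) = 1.07
- 4 v 2, none lost: (212 + 2,862)/(432 + 2,862) = 0.93
- 4 v 2, 2 active deaths lost: (212 + 2,862)/(216 + 2,862) = 1.00

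If the stroke, rehospitalisation and AF-intervention tiers were balanced between arms, they would decide more pairs equally each way and bring these ratios closer to 1.

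**The case against.** The strongest reply is that the gap is narrow. Applying mITT to every efficacy analysis is the protocol's own rule, and the SAP adds only the type of ECG. The protocol takes its AF data from patches, so the added words may simply make the definition operational. The patch is scheduled from Day 1, as is the 12-lead ECG after surgery. One failed patch excludes nobody: any recording by Day 30 qualifies, and the first patch covers only about the first week. Safety and mITT counts by arm show how many are excluded. The safety population includes all dosed participants, with deaths listed and strokes tabulated by arm. The affected endpoints are additional or exploratory, in a Phase 2 study.

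All of this stands as a limit on size. It does not remove the point. The protocol text does not restrict the ECG to the patch, and the change is undeclared. The safety outputs do not rerun the win ratio, and they group participants by treatment received, not by randomised arm. Discontinuation reasons for those excluded are tabulated nowhere.

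A fair objection to the remedy also stands. In length of stay, which ends at death, an early death counts as a short stay. In rehospitalisation, a participant who dies before discharge may count as having no event. Adding these deaths without a rule could score them as good outcomes.

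A reader might go further and infer that the sickest participants are the ones lost, that the loss favours the active arm, or that deaths are hidden from the report. The documents support none of these. They say nothing on who lacks patch data, the trial is double-blind with no stated reason for unequal patch loss, and the deaths remain in the safety listings.

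**Conclusion.** The point holds in a limited form. SAP 6.1 narrows the protocol's mITT set without declaring it, and through SAP 10.0 the narrower set applies to endpoints that need no patch. A dosed participant with no ePatch recording by Day 30 is dropped from the win ratio, from the other patch-free additional and exploratory endpoints, and from the discontinuation tables.

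The size is unknown, probably small and possibly nil. The component ratios of 1.50 and 3.00 rest on an assumed 3 deaths per arm and on loss from one arm only. Equal loss leaves 1.00, and loss from placebo alone moves the ratio the other way. Under the Step 4 assumptions the composite moves far less, to 1.03 or 1.07. The component still matters, because SAP 10.3 reports a win ratio for each component, and with few deaths one or two exclusions can change it visibly.

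The tables should not be read as a forecast, or as evidence that the primary result is at risk. The primary and the patch-derived secondary endpoints need a recording and are not at issue.

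**What to change.** - **Patch-derived endpoints:** keep the ePatch condition.
- **Win ratio:** analyse all randomised and dosed participants by randomised arm. This is wider than the Protocol 9.3 set, which still requires a post-dose ECG.
- **Disposition (SAP 7.0):** tabulate disposition and discontinuation reasons in that same set, and show participants who are in Safety but not in mITT by arm and reason.
- **AF interventions, resource use, rehospitalisation and length of stay:** use the same set, but report in-hospital deaths separately, or add a sensitivity analysis that does not treat death as a short stay or as absence of rehospitalisation.
- **Patient-reported outcomes:** use the same set. It adds only participants who have questionnaire data but no patch data.
- **SAP 16.0:** list the change to the mITT definition, with its rationale.

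The cost is SAP wording and one extra population flag, with no new data. The drawback is that denominators will differ between patch-derived and other endpoints, so each table needs its population labelled.
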